### **8.3. Adverse Events, Serious Adverse Events, and Other Safety Reporting**

The definitions of an AE and an SAE can be found in [Appendix 3](#).

AEs may arise from symptoms or other complaints reported to the investigator by the participant (or, when appropriate, by a caregiver, surrogate, or the participant's legally authorized representative), or they may arise from clinical findings of the Investigator or other healthcare providers (clinical signs, test results, etc.).

The investigator and any qualified designees are responsible for detecting, documenting, and recording events that meet the definition of an AE or SAE and remain responsible to pursue and obtain adequate information both to determine the outcome and to assess whether the event meets the criteria for classification as an SAE or caused the participant to discontinue the study (see [Section 7.1](#)).

During the active collection period as described in Section 8.3.1, each participant will be questioned about the occurrence of AEs in a nonleading manner.

In addition, the investigator may be requested by Pfizer Safety to obtain specific follow-up information in an expedited fashion.

#### **8.3.1. Time Period and Frequency for Collecting AE and SAE Information**

The time period for actively eliciting and collecting AEs and SAEs ("active collection period") for each participant begins from the time the participant provides informed consent, which is obtained before the participant's participation in the study (ie, before undergoing any study-related procedure and/or receiving study intervention), through and including a minimum of 157 calendar days ( $\pm 3$  days) after the last administration of the study intervention.

Follow-up by the investigator continues throughout and after the active collection period and until the AE or SAE or its sequelae resolve or stabilize at a level acceptable to the investigator.

For participants who are screen failures, the active collection period ends when screen failure status is determined.

If the participant withdraws from the study and also withdraws consent for the collection of future information, the active collection period ends when consent is withdrawn.

If a participant permanently discontinues or temporarily discontinues study because of an AE or SAE, the AE or SAE must be recorded on the CRF and the SAE reported using the CT SAE Report Form.

Investigators are not obligated to actively seek information on AEs or SAEs after the participant has concluded study participation. However, if the investigator learns of any SAE, including a death, at any time after a participant has completed the study, and he/she considers the event to be reasonably related to the study intervention, the investigator must promptly report the SAE to Pfizer using the CT SAE Report Form.

#### **8.3.1.1. Reporting SAEs to Pfizer Safety**

All SAEs occurring in a participant during the active collection period as described in [Section 8.3.1](#) are reported to Pfizer Safety on the CT SAE Report Form immediately upon awareness and under no circumstance should this exceed 24 hours, as indicated in [Appendix 3](#). The investigator will submit any updated SAE data to the sponsor within 24 hours of it being available.

#### **8.3.1.2. Recording Nonserious AEs and SAEs on the CRF**

All nonserious AEs and SAEs occurring in a participant during the active collection period, which begins after obtaining informed consent as described in [Section 8.3.1](#), will be recorded on the AE section of the CRF.

The investigator is to record on the CRF all directly observed and all spontaneously reported AEs and SAEs reported by the participant.

#### **8.3.2. Method of Detecting AEs and SAEs**

The method of recording, evaluating, and assessing causality of AEs and SAEs and the procedures for completing and transmitting SAE reports are provided in [Appendix 3](#).

Care will be taken not to introduce bias when detecting AEs and/or SAEs. Open-ended and nonleading verbal questioning of the participant is the preferred method to inquire about AE occurrences.

#### **8.3.3. Follow-Up of AEs and SAEs**

After the initial AE or SAE report, the investigator is required to proactively follow each participant at subsequent visits/contacts. For each event, the investigator must pursue and obtain adequate information until resolution, stabilization, the event is otherwise explained, or the participant is lost to follow-up (as defined in [Section 7.3](#)).

In general, follow-up information will include a description of the event in sufficient detail to allow for a complete medical assessment of the case and independent determination of possible causality. Any information relevant to the event, such as concomitant medications and illnesses, must be provided. In the case of a participant death, a summary of available autopsy findings must be submitted as soon as possible to Pfizer Safety.

Further information on follow-up procedures is given in [Appendix 3](#).

#### **8.3.4. Regulatory Reporting Requirements for SAEs**

Prompt notification by the investigator to the sponsor of an SAE is essential so that legal obligations and ethical responsibilities toward the safety of participants and the safety of a study intervention under clinical investigation are met.

The sponsor has a legal responsibility to notify both the local regulatory authority and other regulatory agencies about the safety of a study intervention under clinical investigation. The sponsor will comply with country-specific regulatory requirements relating to safety reporting to the regulatory authority, IRBs/ECs, and investigators.

Investigator safety reports must be prepared for SUSARs according to local regulatory requirements and sponsor policy and forwarded to investigators as necessary.

An investigator who receives SUSARs or other specific safety information (eg, summary or listing of SAEs) from the sponsor will review and then file it along with the SRSD(s) for the study and will notify the IRB/EC, if appropriate according to local requirements.

#### **8.3.5. Environmental Exposure, Exposure During Pregnancy or Breastfeeding, and Occupational Exposure**

Environmental exposure, occurs when a person not enrolled in the study as a participant receives unplanned direct contact with or exposure to the study intervention. Such exposure may or may not lead to the occurrence of an AE or SAE. Persons at risk for environmental exposure include healthcare providers, family members, and others who may be exposed. An environmental exposure may include exposure during pregnancy, exposure during breastfeeding, and occupational exposure.

Any such exposure to the study intervention under study are reportable to Pfizer Safety within 24 hours of investigator awareness.

##### **8.3.5.1. Exposure During Pregnancy**

An EDP occurs if:

- A female participant is found to be pregnant while receiving or after discontinuing study intervention.
- A male participant who is receiving or has discontinued study intervention exposes a female partner prior to or around the time of conception.

- A female is found to be pregnant while being exposed or having been exposed to study intervention due to environmental exposure. Below are examples of environmental EDP:
  - A female family member or healthcare provider reports that she is pregnant after having been exposed to the study intervention by ingestion, inhalation or skin contact.
  - A male family member or healthcare provider who has been exposed to the study intervention by ingestion, inhalation or skin contact then exposes his female partner prior to or around the time of conception.

The investigator must report EDP to Pfizer Safety within 24 hours of the investigator's awareness, irrespective of whether an SAE has occurred. The initial information submitted should include the anticipated date of delivery (see below for information related to termination of pregnancy).

- If EDP occurs in a participant or a participant's partner, the investigator must report this information to Pfizer Safety on the CT SAE Report Form and an EDP Supplemental Form, regardless of whether an SAE has occurred. Details of the pregnancy will be collected after the start of study intervention and until 157 days ( $\pm 3$  days) after last dose.
- If EDP occurs in the setting of environmental exposure, the investigator must report information to Pfizer Safety using the CT SAE Report Form and EDP Supplemental Form. Since the exposure information does not pertain to the participant enrolled in the study, the information is not recorded on a CRF; however, a copy of the completed CT SAE Report Form is maintained in the investigator site file.

Follow-up is conducted to obtain general information on the pregnancy and its outcome for all EDP reports with an unknown outcome. The investigator will follow the pregnancy until completion (or until pregnancy termination) and notify Pfizer Safety of the outcome as a follow-up to the initial EDP Supplemental Form. In the case of a live birth, the structural integrity of the neonate can be assessed at the time of birth. In the event of a termination, the reason(s) for termination should be specified and, if clinically possible, the structural integrity of the terminated fetus should be assessed by gross visual inspection (unless preprocedure test findings are conclusive for a congenital anomaly and the findings are reported).

Abnormal pregnancy outcomes are considered SAEs. If the outcome of the pregnancy meets the criteria for an SAE (ie, ectopic pregnancy, spontaneous abortion, intrauterine fetal demise, neonatal death, or congenital anomaly in a live-born baby, a terminated fetus, an intrauterine fetal demise, or a neonatal death), the investigator should follow the procedures for reporting SAEs. Additional information about pregnancy outcomes that are reported to Pfizer Safety as SAEs follows:

- Spontaneous abortion including miscarriage and missed abortion;
- Neonatal deaths that occur within 1 month of birth should be reported, without regard to causality, as SAEs. In addition, infant deaths after 1 month should be reported as SAEs when the investigator assesses the infant death as related or possibly related to exposure to the study intervention.

Additional information regarding the EDP may be requested by the sponsor. Further follow-up of birth outcomes will be handled on a case by case basis (eg, follow-up on preterm infants to identify developmental delays). In the case of paternal exposure, the investigator will provide the participant with the Pregnant Partner Release of Information Form to deliver to his partner. The investigator must document in the source documents that the participant was given the Pregnant Partner Release of Information Form to provide to his partner.

#### **8.3.5.2. Exposure During Breastfeeding**

An exposure during breastfeeding occurs if:

- A female participant is found to be breastfeeding while receiving or after discontinuing study intervention.
- A female is found to be breastfeeding while being exposed or having been exposed to study intervention (ie, environmental exposure). An example of environmental exposure during breastfeeding is a female family member or healthcare provider who reports that she is breastfeeding after having been exposed to the study intervention by ingestion, inhalation, or skin contact.

The investigator must report exposure during breastfeeding to Pfizer Safety within 24 hours of the investigator's awareness, irrespective of whether an SAE has occurred. The information must be reported using the CT SAE Report Form. When exposure during breastfeeding occurs in the setting of environmental exposure, the exposure information does not pertain to the participant enrolled in the study, so the information is not recorded on a CRF. However, a copy of the completed CT SAE Report Form is maintained in the investigator site file.

An exposure during breastfeeding report is not created when a Pfizer drug specifically approved for use in breastfeeding women (eg, vitamins) is administered in accord with

authorized use. However, if the infant experiences an SAE associated with such a drug, the SAE is reported together with the exposure during breastfeeding.

### **8.3.5.3. Occupational Exposure**

The investigator must report any instance of occupational exposure to Pfizer Safety within 24 hours of the investigator's awareness using the CT SAE Report Form regardless of whether there is an associated SAE. Since the information about the occupational exposure does not pertain to a participant enrolled in the study, the information is not recorded on a CRF; however, a copy of the completed CT SAE Report Form must be maintained in the investigator site file.

### **8.3.6. Cardiovascular and Death Events**

Not applicable.

### **8.3.7. Disease-Related Events and/or Disease-Related Outcomes Not Qualifying as AEs or SAEs**

Not applicable

### **8.3.8. Adverse Events of Special Interest**

Not applicable.

#### **8.3.8.1. Lack of Efficacy**

This section is not applicable because efficacy is not expected in the study population.

### **8.3.9. Medical Device Deficiencies**

Not applicable.

### **8.3.10. Medication Errors**

Medication errors may result from the administration or consumption of the study intervention by the wrong participant, or at the wrong time, or at the wrong dosage strength.

Exposures to the study intervention under study may occur in clinical trial settings, such as medication errors.

Safety Event	Recorded on the CRF	Reported on the CT SAE Report Form to Pfizer Safety Within 24 Hours of Awareness
Medication errors	All (regardless of whether associated with an AE)	Only if associated with an SAE

Medication errors include:

- Medication errors involving participant exposure to the study intervention;
- Potential medication errors or uses outside of what is foreseen in the protocol that do or do not involve the study participant.

Such medication errors occurring to a study participant are to be captured on the medication error page of the CRF, which is a specific version of the AE page.

In the event of a medication dosing error, the sponsor should be notified within 24 hours.

Whether or not the medication error is accompanied by an AE, as determined by the investigator, the medication error is recorded on the medication error page of the CRF and, if applicable, any associated AE(s), serious and nonserious, are recorded on the AE page of the CRF.

Medication errors should be reported to Pfizer Safety within 24 hours on a CT SAE Report Form **only when associated with an SAE**.

#### 8.4. Pharmacokinetics

Blood samples of approximately 3 mL, to provide a minimum of 1 mL serum, will be collected for measurement of serum concentrations of PF-06823859 as specified in the [SoA](#). Instructions for the collection and handling of biological samples will be provided in the laboratory manual or by the sponsor. The actual date and time (24-hour clock time) of each sample will be recorded.

The actual times may change, but the number of samples will remain the same. All efforts will be made to obtain the samples at the exact nominal time relative to dosing. Collection of samples up to and including 10 hours after dose administration that are obtained within 10% of the nominal time relative to dosing (eg, within 6 minutes of a 60-minute sample) will not be captured as a protocol deviation, as long as the exact time of the collection is noted on the source document and the data collection tool (eg, CRF). Collection of samples more than 10 hours after dose administration that are obtained  $\leq 1$  hour away from the nominal time relative to dosing will not be captured as a protocol deviation, as long as the exact time of the collection is noted on the source document and the data collection tool (eg, CRF). This protocol deviation window does not apply to samples to be collected more than 10 hours after dose administration at outpatient/follow-up visits with visit windows.

Samples will be used to evaluate the PK of PF-06823859. Samples collected for analyses of PF-06823859 serum concentration may also be used to evaluate safety or efficacy aspects related to concerns arising during or after the study, for metabolite identification and/or evaluation of the bioanalytical method, or for other internal **CCI** purposes.

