- h. Check exposure to positive participant, residence or travel in area of high incidence and COVID-19 related signs and symptoms. To be done at each visit.
- i. The testing for COVID-19 pathogen by PCR will be performed within 72 hours prior to admission on Day -1. In addition, a subsequent COVID-19 test will be performed after 4 days (ie, upon completion of 4 × 24 hours in house), or if they develop COVID-19 like symptom.
- j. To be done at least daily during residence and at every follow-up visit after discharge from the CRU.
- k. End of infusion (ie, 1-hour post-dose).

Visit Identifier a Abbreviations used in this table may be found in Appendix 7 .	Screening	CRU Confinement											Follow-Up							ET
		-28 to -2	-1	1				2	3	4	5	8	15	29	43	57	71	100	127	
Days Relative to Day 1	-28 to -2	-1	1				2	3	4	5	8	15	29	43	57	71	100	127	157	-
Visit Window (days)	-	-	-				-	-	-	-	±1	±1	±1	±3	±3	±3	±3	±3	±3	-
Hours After Dose			0 b	1	2	6	12	24	48	72	96	-	-	-	-	-	-	-	-	-

l. Participants with positive results may be requested to return for additional follow-up for up to approximately 3 months after final visit.

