##### 6.1.1. Administration

Intervention Name	PF-06823859 100 mg/mL	Placebo for PF-06823859
ARM Name (group of patients receiving a specific treatment, or no treatment)	Active	Placebo
Type	Biologic	Biologic
Dose Formulation	Solution for Injection	Solution for Injection
Unit Dose Strength(s)	100 mg/mL	0 mg/mL
Dosage Level(s)	900 mg	Placebo
Route of Administration	Intravenous	Intravenous
Use	Experimental	Placebo
IMP or NIMP	IMP	IMP
Sourcing	Provided by the sponsor.	Provided by the sponsor.
Packaging and Labeling	Study intervention will be provided in vials packaged in individual cartons. Each vial and carton will be	Study intervention will be provided in vials packaged in individual cartons. Each vial and carton will

	labeled as required per country requirement.	be labeled as required per country requirement.
--	--	---

Participants will receive study intervention at approximately 0800 hours on Day 1 (plus or minus 2 hours). Study intervention does not require fasting, but it should be noted that the safety laboratory test at Day -1 prior to the study intervention need a fast of at least 4 hours. Investigator site personnel will administer study intervention as a 60-minute intravenous infusion using a calibrated infusion pump. Study medication must not be administered as an IV push or bolus. The infusion rate, amount of volume infused, start and stop time of the infusion will be recorded. Time 0 is the time when the study drug infusion begins. The infusion will be on the opposite arm from PK sampling.

Administer study intervention according to the IP Manual.

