#### **6.1.1.1. Intravenous Infusion Discontinuation**

- If a participant experiences symptoms typical of an allergic reaction, the study drug administration should be discontinued immediately and permanently.
- If a participant experiences symptoms typical of infusion related reactions (eg, lightheadedness, nausea, chills, fever), the study drug infusion should be stopped. At the discretion of the investigator, the infusion can be restarted at a slower rate if symptoms are resolved within 1 hour after the stop of infusion. If symptoms return, then the study drug administration should be discontinued immediately and permanently.
- In the event that there is an infusion interruption, the entire duration of drug infusion, from the initial start of infusion to the completion of infusion, should not exceed 3 hours. Participants will receive appropriate treatment at the discretion of the investigator.

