**Table 1. Definition of Serum PK Parameters for PF-06823859**

Parameter	Definition	Method of determination
$C_{max}$	Maximum serum concentration	Observed directly from data
$C_{max} (dn)$	Dose normalized $C_{max}$	$C_{max}/dose$
$T_{max}$	Time at which $C_{max}$ occurs	Observed directly from data as time of first occurrence
$AUC_{inf}^a$	Area under the serum concentration-time profile from time zero extrapolated to infinite time	$AUC_{last} + (C_{last}*/k_{el})$ , where $C_{last}^*$ is the predicted serum concentration at the last quantifiable time Point estimated from the log-linear regression analysis
$AUC_{inf} (dn)^a$	Dose normalized $AUC_{inf}$	$AUC_{inf}/Dose$
$AUC_{last}$	Area under the serum concentration-time profile from time zero to the time of the last quantifiable concentration ( $C_{last}$ )	Linear/Log trapezoidal method
$AUC_{last} (dn)$	Dose normalized $AUC_{last}$	$AUC_{last}/Dose$
$AUC_{14day}$	Area under the concentration-time profile from time zero to 14 days post-dose (336 hours)	Linear/Log trapezoidal method
$AUC_{28day}$	Area under the concentration-time profile from time zero to 28 days post-dose (672 hours)	Linear/Log trapezoidal method
$t_{1/2}^a$	Terminal half-life	$Log_e(2)/k_{el}$ , where $k_{el}$ is the terminal phase rate constant calculated by a linear regression of the log-linear concentration-time curve
$CL^a$	Clearance	$Dose/AUC_{inf}$
$V_z$	Volume of distribution	$Dose/(AUC_{inf}*k_{el})$

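### The end-of-infusion PK sample is timed from infusion start with a two-sided 6-minute tolerance, so a compliant draw can miss the peak; the effect on Cmax and Tmax is modest and cheap to remove

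*Protocol*

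**What the plan says.** - **Dosing clock.** Protocol 6.1.1 gives study drug "as a 60-minute intravenous infusion using a calibrated infusion pump", and "Time 0 is the time when the study drug infusion begins". The stop time is recorded, but no section uses it to time a PK sample.
- **The peak sample.** Footnote k of the Schedule of Activities describes the 1-hour PK draw as "End of infusion (ie, 1-hour post-dose". The next draws are at 2, 6 and 12 hours.
- **The tolerance.** Under Protocol 8.4, samples up to 10 hours after dosing that are "obtained within 10% of the nominal time relative to dosing" are not deviations. The worked example is "eg, within 6 minutes of a 60-minute sample) will not be captured as a protocol deviation". The same section says "All efforts will be made to obtain the samples at the exact nominal time relative to dosing".
- **Interruption.** Protocol 6.1.1.1 allows a stopped infusion to be restarted more slowly, with a total duration that "should not exceed 3 hours".
- **Parameters.** Cmax and Tmax are primary PK parameters (Protocol 3). In Table 1, Cmax is taken directly from the data, and Tmax likewise: "Observed directly from data as time of first occurrence".
- **SAP.** Concentrations are summarised by nominal time (SAP 6.1.2). SAP 5.3.1 and 5.3.2 allow discretionary handling of timing deviations, of events that affect the profile, and of parameters known to be biased. Neither has a rule for a sample taken before the infusion ended.

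**The concern.** During a constant-rate infusion of a long-lived antibody, concentration rises almost linearly until the pump stops. A draw before the stop is on the rising limb, and half of the permitted range lies there. Using actual sampling times corrects the time stamp but not the concentration, so an unsampled peak stays unsampled. When an infusion overruns or is interrupted, footnote k asks for two different times at once, and a site cannot tell which to follow.

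What is at stake is the accuracy of Cmax and Tmax, and of the 1-hour mean concentration, in about 10 actively treated participants whose profiles are to be compared with non-Chinese data. A Tmax difference produced by draw timing could be mistaken for a population difference. No test or error rate is involved, because the analysis is descriptive.

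**Working it through.** **1. The plan's own figure.** 10% × 60 min = 6 min, which reproduces the example in 8.4. The compliant range is 54–66 min from infusion start. At 54 min, 54/60 = 90% of the dose has been given.

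**2. Model.** For an infusion of duration T, C(t) = Σ wᵢ · [1 − exp(−kᵢ·min(t,T))]/(kᵢT) · exp(−kᵢ·max(t−T,0)), with kᵢ = ln 2 / half-lifeᵢ. The terminal half-life is 157/5 = 31.4 days, because Protocol 10.4.2 equates 157 days with 5 terminal half-lives. The distribution half-life and its weight are not in the documents. They are assumed, and a range is shown.

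**3. A 54-minute draw, 60-minute infusion, no assay noise.** Observed Cmax is the larger of C(54 min) and C(2 h), relative to the level at the end of infusion.

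| Distribution half-life (weight) | C(54 min)/C(end) | C(2 h)/C(end) | Observed Tmax | Cmax shortfall |
|---|---|---|---|---|
| none (one compartment) | 0.900 | 0.999 | 2 h | 0.1% |
| 96 h (30%) | 0.900 | 0.997 | 2 h | 0.3% |
| 24 h (50%) | 0.901 | 0.985 | 2 h | 1.5% |
| 12 h (70%) | 0.902 | 0.961 | 2 h | 3.9% |
| 2 h (30%) | 0.904 | 0.921 | 2 h | 7.9% |
| 2 h (50%) | 0.907 | 0.865 | 0.9 h | 9.3% |
| 1 h (70%) | 0.918 | 0.686 | 0.9 h | 8.2% |

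With slow distribution the 2-hour sample is a good backstop for Cmax, and Tmax moves to 2 h. With fast distribution the early draw usually stays the highest, Tmax reads 0.9 h, and Cmax loses 8–10%.

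**4. Mean at 1 hour.** If draws were spread evenly over 54–66 min, half would be early, by 3 min on average. The mean would be low by about ½ × 3/60 = 2.5%.

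**5. Overrun and interruption.** With one compartment, an exact 60-minute draw is at 97%, 92% or 86% of the peak if the infusion takes 62, 65 or 70 min. At a constant rate over 3 h, the 1-hour and 2-hour draws are at 33% and 67% of the peak. Cmax is then read at 6 h, 3 h after the stop, where the level is 0.957–0.992 of the peak under slow distribution (24–96 h, 30–50%). That is 1–4% low.

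**6. What re-anchoring changes.** Simulated under slow distribution (24–96 h, 30–50%), with draws uniform in the window, samples at about 1, 2, 6 and 12 h, and an assumed assay CV. The table gives the share of participants whose Tmax falls after the first sample.

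| Assay CV | 54–66 min | 60–66 min | Reduction (points) |
|---|---|---|---|
| 2% | 56–75% | 31–58% | 17–25 |
| 5% | 60–77% | 46–67% | 10–13 |
| 10% | 64–77% | 57–71% | 6–7 |

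**7. Cost of a late draw.** C(66 min)/C(60 min) is 0.996–0.9999 when the distribution half-life is 12 h or longer, and 0.958 in the most extreme case assumed (1 h, 70%). A one-sided window loses little.

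**The case against.** The strongest reply is that 8.4 asks for the exact nominal time and uses the 10% only to decide what counts as a deviation. Footnote k tells staff that they are sampling the end of infusion, and for an uninterrupted 60-minute pump infusion its two labels agree. The laboratory manual, which is not available here, may already settle the order of pump stop and draw. The SAP lets the analyst set aside affected concentrations, profiles or parameters. The outputs are descriptive, and Tmax is reported only as N, median, minimum and maximum.

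Most of this stands, and it limits the point. Even spread over the window is an assumption that probably overstates early draws. The SAP provisions help but are discretionary, and no visible section requires the draw to follow the stop.

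A reader might also infer that early draws alone push Tmax to 2 h in nearly half of participants, and that the fix would remove this. The noise-free arithmetic does give that. With C(2 h)/C(end) of 0.985–0.997, a draw more than m = 0.2–0.9 min early makes the 2-hour sample the maximum, so (6 − m)/12 = 43–49%. The documents do not support relying on it. It needs evenly spread draws, slow distribution and a perfect assay. The profile after the infusion is nearly flat under these assumptions, so assay noise decides much of Tmax under either window.

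**Conclusion.** The gap is real: a compliant peak sample can precede the end of infusion, and footnote k is ambiguous whenever the infusion does not last 60 minutes. The consequence is modest. At the edge of the window Cmax is about 0.3–1.5% low under slow distribution (half-life 24–96 h) and up to about 10% low under fast distribution (about 1–2 h). Tmax tends to move to 2 h in the first case and to read 0.9 h in the second. AUCs barely change, because they use actual times and the affected interval is short. Correcting the anchor lowers the share with a later Tmax by about 6–25 points, given evenly spread draws, slow distribution and an assay CV of 2–10%. Distribution half-life, assay CV and draw spread are all assumptions. This is an inexpensive improvement, not a threat to the study's conclusions.

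**What to change.** - **Footnote k and Protocol 8.4.** Time this one sample from the recorded actual stop of the infusion, with a window of 0 to +6 minutes. Leave the other sampling windows unchanged.
- **Interrupted or slowed infusions.** Reconcile footnote k and 8.4 with 6.1.1.1, so that the site knows when the end-of-infusion sample is due. It can fall after the nominal 2-hour sample.
- **SAP 6.1.2.** State that this sample is summarised as end of infusion and, when the infusion did not end at about 1 hour, is left out of the nominal 1-hour concentration summary. Without this rule, re-anchoring would put a draw taken as late as about 3 h into the 1-hour row.

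The cost is one protocol sentence, mirrored in the laboratory manual, and one SAP sentence. No extra sample is needed and the stop time is already recorded. Protocol 8.4 also lets documented, approved changes in assessment timing be made without a protocol amendment.
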